2.3.1. Risk Assessment

Potential Risk of Clinical Significance	Summary of Data/Rationale for Potential Risk for Study Drug BLD-2660	Mitigation Strategy
Elevated troponin	Transient, asymptomatic mild troponin elevation was observed in 2 healthy volunteers in Phase 1; there were no associated clinical, electrocardiographic or imaging findings and these changes resolved without sequelae despite continued dosing. Biologically, calpain inhibition has not been associated with cardiac toxicity in animal models, and there was no evidence of cardiac toxicity in acute and chronic toxicology studies.	Safety cardiac monitoring protocol (see Section 10.5)

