
 Additional efficacy outcomes 	
 Mortality rate during the 28-day study period following enrollment Time to hospital discharge readiness Proportion of subjects ready to be discharged from the hospital during the 28-day study period following enrollment Proportion of subjects with resolution of fever below entry criteria for 24 hours (as defined in Section 5.1.1) by Day 10 in subjects with fever at baseline Time to resolution of fever below entry criteria for 24 hours (as defined in Section 5.1.1) in subjects with fever at baseline Duration (in days) of remdesivir use in subjects starting remdesivir within 24 hours of first dose of BLD-2660 Change from baseline to Days 10, 14, 21 and 28 in clinical status outcome using a 6-point ordinal scale (Section 8.1.3) Proportion of subjects reporting each 6-point ordinal scale of the clinical status outcome assessment Change from baseline to Days 5, 10, 14, 21 and 28 in NEWS score Change from baseline to Days 10, 14, 21 and 28 in IL-6 and D-dimer
Exploratory	

 Other efficacy outcomes 	
 Proportion of subjects who require mechanical ventilation after study entry Number of ventilator-free days to Day 21 Proportion of subjects with ICU transfer and/or ventilator dependence during the 28-day study period following enrollment

Objectives	Endpoints
	
 • The time to a NEWS of ≤ 2 and maintained for 24 hours • Change in NEWS from baseline to Days 3, 5, 8, 10, 14, 21 and 28 in NEWS

 • To evaluate antiviral activity of BLD-2660 in the same population 	
 • Proportion of subjects who are SARS--CoV-2 virus free by Day 10/EOT or hospital discharge, whichever is sooner • Time to eradication of SARS-CoV-2 • Change from baseline in SARS-CoV-2 viral load at Days 5, 10, 14, and 28

 • Other safety outcomes 	
 • Clinically relevant changes from baseline in electrocardiogram (ECG), and clinical laboratory values at each post baseline timepoint • Proportion of subjects with clinically significant drug-related troponin elevations that have repeat elevation upon confirmatory testing as adjudicated by the DMC while continuing on study drug during the 10-day treatment period

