10.5. Appendix 5: Cardiac Monitoring Protocol

All troponin elevations and cardiac AEs and SAEs will be reviewed by the DMC.

Subjects with elevated troponins will be questioned regarding occurrence of any cardiac symptoms. The symptoms will be evaluated by a study investigator and a consulting physician independent of the investigator team who will recommend whether any additional studies should be performed. In addition, during the evaluation period:

1. Study drug could be withheld, at the discretion of the investigator
2. Serum troponin, Creatine Kinase-Myocardial Band (CK-MB), myoglobin, comprehensive metabolic panel (including AST) will be obtained and echocardiogram and ECG performed and interpreted
3. Detailed history of potential causes of troponin elevation should be obtained
4. Additional work up will be initiated per the Investigator's discretion and cardiology consultant

If work up is negative, as determined by Investigator and/or Medical Monitor, no further action is required and, if the study drug had been stopped, it may be restarted.

If work up is positive for a cardiac source, the DMC will review and determine whether the study drug should be permanently discontinued and advise on any next steps, if any.

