1.1. Objectives and Endpoints

Objectives	Endpoints
Primary	

 To evaluate clinical benefit of BLD-2660 in hospitalized adults with recently diagnosed SARS-CoV-2 infection 	
 Time to recovery as defined by no longer requiring oxygen support or hospital discharge, whichever occurs first

 To evaluate improvement in oxygenation in hospitalized adults with COVID-19 treated with BLD-2660 	
 Change from baseline to Day 10 or hospital discharge, if sooner, in the ratio of peripheral hemoglobin oxygen saturation to fraction of inspired oxygen (SpO₂/FiO₂)
Secondary	

 To evaluate the safety and tolerability of BLD-2660 in the same population 	
 Incidence of TEAEs and serious adverse events (SAEs)

 To evaluate improvement in Biomarkers 	
 Change from baseline to Days 10/EOT, 14, 21 and 28 in serum calprotectin

 Additional efficacy outcomes 	
 Time to hospital discharge readiness Proportion of participants reporting each 6-point ordinal scale of the clinical status outcome assessment Change from baseline to Days 10/EOT, 14, 21 and 28 in IL-6 and D-dimer

Objectives	Endpoints
Exploratory	

 Other efficacy outcomes 	
 Proportion of participants who require mechanical ventilation after study entry

 To evaluate antiviral activity of BLD-2660 in the same population 	
 Change from baseline in SARS-CoV-2 viral load at Days 5, 10/EOT, 14, and 28

 Other safety outcomes 	
 Clinically relevant changes from baseline in electrocardiogram (ECG), and clinical laboratory values at each post baseline time point Proportion of participants with clinically significant drug-related troponin elevations that have repeat elevation upon confirmatory testing as adjudicated by the DMC while continuing study drug during the 10-day treatment period

 To assess population pharmacokinetics (PK) characteristics of BLD-2660 	
 BLD-2660 plasma concentrations

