5.8.3. Safety Labs

This study will be using local labs instead of central labs. Descriptive summary statistics of the observed values and change from baseline values for hematology, chemistry and urinalysis data at screening, baseline and each post-baseline visit (i.e., Day 5/Discharge, Day 10/Discharge, 14, 21 and 28) will be presented by treatment group. Boxplots will be used to display the distribution of the observed values over time, by treatment group.

Participants with clinically significant values for any safety labs are to be reported as an AE and therefore clinically significant laboratory findings will be interpreted from the AE summaries.

A listing of participants with clinically significant drug-related troponin elevations that have repeat elevation upon confirmatory testing as adjudicated by the DMC while continuing study drug during the 10-day treatment period will be provided.

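### The troponin endpoint counts only repeat elevations seen on study drug, yet drug may be withheld while the repeat is taken, and the SAP names no by-arm troponin summary to fill the gap

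*SAP*

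**What the plan says.** Protocol 2.3.1 has a single row, elevated troponin. The reason given is that "Transient, asymptomatic mild troponin elevation was observed in 2 healthy volunteers in Phase 1".

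Protocol Section 3 and SAP 1.1 both list, among the other (exploratory) safety outcomes, the proportion of subjects with clinically significant, drug-related troponin elevations that repeat on confirmatory testing. The protocol adds "as adjudicated by the DMC while continuing on study drug during the 10-day treatment period"; the SAP wording is nearly identical: "as adjudicated by the DMC while continuing study drug during the 10-day treatment period".

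Protocol Appendix 5 sets out what happens after an elevated troponin. During the evaluation period "Study drug could be withheld, at the discretion of the investigator". In that same period the tests to be obtained begin with "Serum troponin, Creatine Kinase-Myocardial Band (CK-MB), myoglobin, comprehensive metabolic panel". If the work-up is negative, "if the study drug had been stopped, it may be restarted". If it points to a cardiac source, the DMC decides whether drug is stopped for good.

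SAP 5.8.3 plans this output for the endpoint: "A listing of participants with clinically significant drug-related troponin elevations that have repeat elevation upon confirmatory testing", with the same on-drug condition. Its by-visit tables are described as "Descriptive summary statistics of the observed values and change from baseline values for hematology, chemistry and urinalysis data". Protocol Table 8 places troponin under other laboratory assessments, outside those three groups. The Schedule of Activities draws troponin at baseline, daily, and on Days 10, 14, 21 and 28.

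**The concern.** The endpoint is conditioned on something that happens after randomization and that the outcome itself can set off. A raised troponin starts an evaluation, the evaluation permits a hold, and a hold before the repeat sample can take the subject out of the numerator. The count can then look low partly because sites acted on what they saw.

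Early discharge has a similar effect. Study drug is given only in hospital, so an elevation confirmed after a discharge before Day 10 is not on drug either.

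The second difficulty is attribution. A case must be judged drug-related, and Protocol 10.3.3 reserves that label for events not reasonably explained by the subject's clinical state or other treatments. In hospitalized COVID-19 patients an alternative explanation is often available, so case-by-case judgement is weak evidence in either direction. Comparing all elevations between randomized arms does not depend on that judgement, and the SAP does not name such a comparison. At stake is how well the trial can describe the one risk that the protocol singles out.

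**Working it through.** **Passages side by side**

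1. *What must be true to count.* The elevation is clinically significant, drug-related, repeated on confirmatory testing and adjudicated by the DMC, with the subject on study drug within the 10-day period (Protocol Section 3; SAP 1.1). The natural reading ties the on-drug condition to the repeat elevation. The text does not say whether a temporary hold breaks it.
2. *What may happen first.* Appendix 5 puts the permission to withhold and the further troponin sample in the same evaluation period, with no order between them and no severity criterion for a hold.
3. *What the SAP produces.* SAP 1.1 states a proportion; SAP 5.8.3 delivers a listing. The by-visit laboratory tables name hematology, chemistry and urinalysis only.
4. *What else could catch a case.* SAP 5.8.3 sends clinically significant safety laboratory values to the adverse event tables, SAP 5.8.2 tabulates those by arm regardless of relationship, and Protocol 8.3.1 collects events to Day 28. Appendix 5 has the DMC review every elevation. However, Protocol 10.3.1 excludes from the adverse event definition abnormal findings associated with the underlying disease, unless judged more severe than expected.

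**Illustration of size**

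The documents state no rate for this endpoint, so there is no figure to reproduce. Let *p* be the true rate of elevations that would otherwise qualify, and *w* the share whose drug is held before the repeat test. Assume that a hold disqualifies the case. Then:

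- counted rate = *p*(1 − *w*)
- P(no case counted in *n*) = (1 − *p*(1 − *w*))^*n*

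The arm sizes are 80 active and 40 control (SAP Table 1). The values of *p* and *w* are assumptions. With *p* = 10% active and 5% control, expected counts are:

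| *w* active / control | Active counted | Control counted | Difference (points) |
|---|---|---|---|
| 0% / 0% | 8.0 of 80 | 2.0 of 40 | 5.0 |
| 25% / 25% | 6.0 | 1.5 | 3.8 |
| 50% / 50% | 4.0 | 1.0 | 2.5 |
| 75% / 75% | 2.0 | 0.5 | 1.3 |
| 75% / 25% | 2.0 | 1.5 | −1.3 |

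For example, at 50% in both arms: 0.10 × 0.5 − 0.05 × 0.5 = 0.025.

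With *p* = 5% active, the chance that no active case is counted is:

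- *w* = 0: 0.95^80 = 1.7%
- *w* = 50%: 0.975^80 = 13.2%
- *w* = 75%: 0.9875^80 = 36.6%

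**What the proposed table could show.** With 8 of 80 against 2 of 40, the standard error of the difference is √(0.10 × 0.90/80 + 0.05 × 0.95/40) = 0.048. The 95% interval is 5.0 ± 9.4 points, about −4.4 to 14.4. The table would describe the risk without the filter; it would not settle it.

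**The case against.** The case on the other side has real content.

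- **The on-drug condition has a rationale.** The Phase 1 elevations resolved while dosing continued (Protocol 2.3.1). Asking whether elevation repeats under continued dosing tests that observation, and a treatment-period endpoint naturally leaves out Days 14, 21 and 28. This stands, and it is why the existing endpoint should be kept.
- **Withholding is discretionary and reversible.** A reader might infer that the most concerning cases drop out systematically. The documents do not support that: no severity criterion is attached to a hold, drug may be restarted, and permanent discontinuation is decided after a work-up that already includes a troponin sample. Cases can drop out; nothing says that they will, or which ones.
- **Other routes exist.** A reader might also infer that troponin is never compared between arms. That goes too far. Protocol 9.4.3 says that laboratory evaluations will be summarized by treatment and time point, which can be read to include troponin. The by-arm adverse event tables remain, and the SAP's table specifications are in a separate document not available here. These routes are still incomplete: SAP Section 1 gives the SAP precedence, its laboratory section does not name troponin, disease-attributed abnormalities may not be reported as adverse events, and DMC review is oversight rather than a reported analysis.
- **The numbers rest on assumptions.** True. The reversal of sign also needs withholding to differ sharply by arm, which is hard to expect in a double-blind trial. It marks an extreme and is not a forecast.

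**Conclusion.** The concern holds in a limited form. The endpoint and Appendix 5 do not fit together: a confirmed elevation can be excluded through a hold that it prompted, and the documents leave the classification of held or restarted subjects open. The SAP then replaces the stated proportion with a listing under the same filter and names no by-arm troponin summary.

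The loss is confined to this endpoint and its listing. Because the adverse event tables and the DMC can still pick up clinically significant elevations, the safety signal is diluted, not lost.

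The size cannot be fixed from the documents. If a hold disqualifies a case, the counted rate falls in proportion to the share withheld: not at all at 0%, by half at 50%, and entirely at 100%. If a hold is read as not interrupting treatment, this particular loss disappears, but the filters on attribution and on the treatment period remain.

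Severity is moderate. The endpoint is exploratory and all safety analyses are descriptive (SAP 5.8), but the risk is the only one in the protocol's risk table and the repair is cheap.

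**What to change.** In SAP 1.1 and 5.8.3, and in Protocol Section 3 so that the two documents stay aligned:

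1. Add a descriptive table by arm of the number and proportion of subjects with any post-baseline troponin above the local upper limit of normal (ULN), and with a repeat elevation. Count from first dose through Day 28, regardless of whether drug was continued, held, stopped or completed, and regardless of attributed cause. Give the risk difference with its 95% confidence interval.
2. Flag drug status at the repeat test (continuing, held, restarted, stopped, completed or discharged), and state which of these satisfy the existing on-drug condition.
3. Add troponin to the by-visit laboratory summaries, as multiples of the local ULN because local laboratories are used. This assumes that local reference limits are in the database.
4. Keep the DMC-adjudicated on-drug endpoint as supportive, reported as the proportion that SAP 1.1 states, together with the listing.

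The endpoint wording and Appendix 5 must be reconciled. This is a matter of classification in the analysis; no change to the withholding rules is proposed.

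The cost is SAP and protocol wording, one new table and an extra parameter in the by-visit summaries. All the samples are already scheduled. The reported troponin rate may look less favourable, since elevations due to disease will be included in both arms. The change should be made before database lock.

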1.2. Study Design

This is a Phase 2 randomized, double-blind, placebo-controlled multicenter study designed to evaluate BLD-2660 as add-on to standard of care (SOC) therapy in hospitalized participants with recently diagnosed COVID-19 compared to SOC treatment.

The study will include a Screening period, a Treatment period, and a Follow-up period.

After signing informed consent form (ICF), potential candidates who are hospitalized for confirmed infection with SARS-CoV-2 will undergo additional screening procedures.

On Day 1, eligible participants will be randomized in 2:1 ratio to one of 2 treatment groups, active or control, as shown in Table 1. Randomization will be stratified by remdesivir at study entry. All participants will receive study drug in combination with SOC over 10 days (through Day 10/end of treatment) or until hospital discharge, if sooner. Participants will be followed for at least 18 days after the last dose of study drug on Days 14, 21 and 28. Participants will be contacted 60 days post-study to collect information on mortality and forced vital capacity (FVC).

CONFIDENTIAL

Statistical Analysis Plan [Version 3.0]

Table 1: Treatment Groups

Treatment Group	Dose Level, Schedule and Route of administration	Number of participants
Active	BLD-2660 900 mg twice per day (BID), oral + SOC	80
Control	Matching placebo, BID, oral + SOC	40

For each participant, the study duration for each study period is expected to last as follows:

Study Period	Duration
Screening period	Up to 3 days
Treatment period	10 days
Treatment Follow-up period	18 days
Post study follow-up period	32 days

Interim analyses are planned when approximately 25%, 50% and 75% of participants have completed the study for the purpose of reviewing safety data and for the purpose of early stopping for efficacy or futility. At the 50% interim analyses, the sample size may be increased.

The final analysis will occur once the last participant enrolled completes the end of study follow-up visit. Data from the post study follow-up visit regarding FVC will be included in the final databased after the final analysis has been completed.

2. Statistical Hypotheses

Two primary statistical hypotheses will be tested. The study will be declared a success if either of the hypotheses are statistically significant. As this is a phase 2 study, no adjustment for multiplicity will be made for having two co-primary hypotheses.

Hypothesis 1: Will evaluate clinical benefit in hospitalized adult participants with recent SARS-CoV-2 infection. The primary endpoint is time to recovery as defined by no longer requiring oxygen support or hospital discharge, whichever occurs first. The null and alternative hypotheses are:

- H_0 (null): Hazard Ratio (BLD2660/Placebo) ≥ 1 , indicating that treatment does not reduce the time to recovery compared to placebo control
- H_1 (alternative): Hazard Ratio (BLD2660/Placebo) < 1 , indicating that treatment does reduce the time to recovery compared to placebo control

Hypothesis 2: Will evaluate improvement in oxygenation in hospitalized adult participants with recent SARS-CoV-2 infection at the time of discharge, or Day 10, if they are still hospitalized. The primary endpoint is the change from baseline to Day 10 or hospital discharge if sooner in the ratio of hemoglobin oxygen saturation to inspired oxygen fraction (SpO_2/FiO_2). The null and alternative hypotheses are:

- H_0 (null): Mean Treatment Difference (BLD2660 minus Placebo) ≤ 0 , indicating that treatment does not improve the ratio of hemoglobin oxygen saturation to inspired oxygen fraction (SpO_2/FiO_2) at the time of discharge or Day 10 if they are still hospitalized, compared to placebo control
- H_1 (alternative): Mean Treatment Difference (BLD2660 minus Placebo) > 0 , indicating that treatment does improve the ratio of hemoglobin oxygen saturation to inspired oxygen fraction (SpO_2/FiO_2) at the time of discharge or Day 10 if they are still hospitalized, compared to placebo control

3. Sample Size Determination

Time to clinical improvement

A randomized, double-blind, placebo-control study evaluating remdesivir in 1063 hospitalized participants with COVID-19 reported 606 recoveries, with a median time to recovery of 11 days and 15 days in the remdesivir and placebo groups, respectively (remdesivir package insert). Recovery was defined as the first day on which the participant satisfies one of the following 3 categories from the ordinal scale: 1) Hospitalized, not requiring supplemental oxygen - no longer requires ongoing medical care; 2) Not hospitalized, limitation on activities and/or requiring home oxygen; 3) Not hospitalized, no limitations on activities (<https://clinicaltrials.gov/ct2/show/NCT04280705>).

Assuming the median time to clinical improvement, defined as no longer requiring oxygen support or hospital discharge whichever occurs first, will be 12-15 days in the placebo group, and that at least 75 of the planned 120 participants enrolled meet the clinically improved criteria, the study will have at least 80% power to detect a 50% reduction in the time to clinical improvement, (i.e., hazard ratio[BLD2660/Placebo] of 0.5) with a two-sided 5% significance level.

The total number of events (d) is estimated based on the following formula

$$d = \frac{(z_{\alpha/2} + z_{\beta})^2}{\pi(1 - \pi)\theta^2}$$

where $z_{\alpha/2}$ and z_{β} are the value from a standard normal distribution, π is the proportion of participants randomized to control, $1 - \pi$ is the proportion of participants randomized to active and θ is the inverse of the log hazard ratio, as we are modeling improvement. The total number of participants is then calculated as the number of events divided by the probability of observing the event during the study. For this study $\alpha = 5\%$, $\beta = 20\%$, $\pi = 1/3$ and $\theta = 1/\log(0.5)$ and the probability of observing an event is 0.60.

Change from baseline to Day 10 or hospital discharge if sooner in the ratio of hemoglobin oxygen saturation to inspired oxygen fraction (SpO₂/FiO₂).

A prospective observational cohort study of non-intubated moderate to severe ARDS participants (Ding, 2020) reported the partial pressure of oxygen (PaO₂)/FiO₂ ratio for 10 participants, which gave a mean and standard deviation of 147 ± 46 mm Hg. Converting to a SpO₂/FiO₂ ratio gives a mean and standard deviation of 192 ± 39 using the equation reported by Rice et al. (2007) (Rice, 2007).

Assuming a standard deviation of 40 in the SpO₂/FiO₂ ratio, a sample size of 120 participants (80 active, vs 40 control) will provide approximately 90% power to detect a treatment difference in the SpO₂/FiO₂ ratio of 25 or greater, based on a two-sample t-test with a two-sided 5% significance level.

CONFIDENTIAL

Statistical Analysis Plan [Version 3.0]

The total number of participants (N) is estimated based on the following formula

$$N = \frac{(z_{\alpha/2} + z_{\beta})^2}{\pi(1 - \pi)\theta^2}$$

where $z_{\alpha/2}$ and z_{β} are the value from a standard normal distribution, π is the proportion of participants randomized to control, $1 - \pi$ is the proportion of participants randomized to active and θ is the standardized effect size we wish to detect. For this study $\alpha = 5\%$, $\beta=10\%$, $\pi=1/3$ and $\theta=0.625$ (i.e., $25/40$).

4. Analysis Sets

For purposes of analysis, the following populations are defined:

Population	Description
Enrolled	All randomized participants
Full Analysis Set (FAS)	All randomized participants who receive at least one dose of study drug. This population will be used for all efficacy analyses
Modified Intent to Treat (MITT)	All randomized participants who receive at least one dose of study drug and one post baseline assessment of the SpO ₂ /FiO ₂ ratio. This population will be used for the primary and secondary endpoints related to improvement in SpO ₂ /FiO ₂ ratio.
Per Protocol Analysis Set (PP)	All randomized participants who receive at least 6 doses of study drug without any major protocol violations that would impact the assessment of the primary efficacy endpoints. This population will be used for efficacy analyses of the primary efficacy endpoints
Safety Analysis Set	All enrolled participants who receive any study drug
PK Analysis Set	All enrolled participants who receive any study drug and have plasma concentration data

5. Statistical Analyses

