9.2. Sample Size Determination

Time to clinical improvement

A randomized, double-blind, placebo-control study evaluating remdesivir in 1063 hospitalized patients with COVID-19 reported 606 recoveries, with a median time to recovery of 11 days and 15 days in the remdesivir and placebo groups, respectively (remdesivir package insert). Recovery was defined as the first day on which the subject satisfies one of the following 3 categories from the ordinal scale: 1) Hospitalized, not requiring supplemental oxygen - no longer requires ongoing medical care; 2) Not hospitalized, limitation on activities and/or requiring home oxygen; 3) Not hospitalized, no limitations on activities (<https://clinicaltrials.gov/ct2/show/NCT04280705>).

Assuming the median time to clinical improvement, defined as no longer requiring oxygen support or hospital discharge whichever occurs first, will be 12-15 days in the placebo group, and that at least 75 of the planned 120 subjects enrolled meet the clinically improved criteria, the study will have at least 80% power to detect a 50% reduction in the time to clinical improvement, (i.e., hazard ratio of 0.5).

Change from baseline to Day 10 or hospital discharge if sooner in the ratio of hemoglobin oxygen saturation to inspired oxygen fraction (SpO_2/FiO_2).

A prospective observational cohort study of non-intubated moderate to severe ARDS patients (Ding, 2020) reported the partial pressure of oxygen (PaO_2)/ FiO_2 ratio for 10 patients, which gave a mean and standard deviation of 147 ± 46 mm Hg. Converting to a SpO_2/FiO_2 ratio gives a mean and standard deviation of 192 ± 39 using the equation reported by Rice et al. (2007) (Rice, 2007).

Assuming a standard deviation of 40 in the SpO_2/FiO_2 ratio, a sample size of 120 subjects (80 active, vs 40 control) will provide approximately 90% power to detect a treatment difference in

the SpO₂/FiO₂ ratio of 25 or greater, based on a two-sample t-test with a two-sided 5% significance level

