3.0	22 October 2020	
Added additional details on how to derive FiO2 values based on oxygen flow rates.
 
Changed IL-6 sub-group analysis from > ULN to > median,
	
eCRFs collected flow rate or FiO2. Additional details on how to derive FiO2 were needed for programming.
 
IL-6 values do not have normal ranges

1. Introduction

This Statistical Analysis Plan (SAP) contains a more technical and detailed elaboration of the principal features of the analysis described in the protocol and includes detailed procedures for executing the statistical analysis. This SAP should be used in conjunction with the protocol. If there are any discrepancies between the protocol and SAP, this SAP will prevail. Any deviations from this SAP that are implemented in the final analysis will be documented with sound clinical and statistical rationale in the Clinical Study Report (CSR). In the event of any changes to the primary endpoints or analyses, these changes will be documented through a protocol amendment, consistent with ICH E9.

A separate document contains the table, figure and listing specifications and any example programming codes.

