5.1. General Considerations

The following is a list of general reporting conventions:

- Percentages will be based on the number of participants in the analysis set unless otherwise indicated.
- Categorical variables will be summarized using counts (n) and percentages (%) and will be presented in the form of n (%).
- Percentages will be reported to 1 decimal place.
- Continuous data will be summarized using the mean, standard deviation (SD), median, minimum, 25th and 75th percentiles, maximum, and number of participants with data.
- Means and medians will be reported at 1 more significant digit than the precision of the data. Standard deviations and confidence intervals will be reported at 2 more significant digits than the precision of the data. Quartiles, minima and maxima will be reported to the same level of precision as the original observations.
- The median will be reported as the average of the 2 middle numbers if the dataset contains even numbers.
- No preliminary rounding should be performed; rounding should only occur after analysis. To round, consider digit to right of last significant digit: if < 5 , then round down; if ≥ 5 , then round up.
- All p-values will be 1-sided and reported to 3 decimal places (e.g., 0.XXX). Values < 0.001 will be reported as < 0.001 .

If departures from these general conventions are present in the specific evaluations sections of this SAP, then those conventions will take precedence over these general conventions.

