5.5. Primary Endpoint(s) Analysis

5.5.1. Definition of Endpoint(s)

Time to Clinical Improvement

Time to clinical improvement will be derived as the earliest date of either not requiring oxygen support or hospital discharge, minus the date of randomization. Participants who die or withdraw from the study prior to observing clinical improvement will be censored on day 28. Participants will be censored on day 28, if clinical improvement has not been observed by this time point. If a participant discontinues study drug early, they will still be assessed for this endpoint until one of the above criteria (i.e., clinical improvement, death/withdrawal, day 28 visit without clinical improvement) is met.

Change from baseline to Day 10 or hospital discharge if sooner, in the ratio of hemoglobin oxygen saturation to inspired oxygen fraction (SpO₂/FiO₂)

SpO₂ and FiO₂ will be collected twice daily while a participant is in hospital. The average of the twice daily SpO₂/FiO₂ ratio will be used for all derivations. If only a single ratio is collected, that single ratio for that day will be used. Once discharged, only a single ratio will be used in the derivations. Participants who are discharged prior to day 10, will have their end of treatment assessment, mapped to day 10.

The SpO₂ value will be recorded on the eCRF. To derive the FiO₂ value, oxygen flow rate as collected on the eCRF will be converted to FiO₂ using the following table.

Method	O2 Flow rate (l/min)	Estimated FiO2 (%)
Nasal cannula	1	24
	2	28
	3	32
	4	36
	5	40
	6	44
Nasopharyngeal catheter	4	40
	5	50
	6	60
Face mask (Simple Mask)	5	40
	6-7	50
	7-8	60
Face mask with reservoir (non-rebreather face mask)	<6	Follow nasal cannula
	6	60
	7	70
	8	80
	9	90
	10	95
	>10	100
Venturi Mask	4	28
	6	31
	8	40
	10	50

The change from baseline to Day 10 or hospital discharge if sooner, in the ratio of hemoglobin oxygen saturation to inspired oxygen fraction (SpO₂/FiO₂) will be derived by taking the SpO₂/FiO₂ ratio at the earlier of day 10 or hospital discharge and subtracting the baseline SpO₂/FiO₂ ratio. Missing data will be assumed to be missing at random and this endpoint will be analyzed using likelihood-based methods, therefore missing data will be maintained as missing.

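### SAP Hypothesis 1 states the recovery hazard ratio in the wrong direction, so its inequality contradicts its own explanation for a test reported one-sided

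*SAP*

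**What the plan says.** SAP 5.5.1 defines the endpoint by a good outcome: "Time to clinical improvement will be derived as the earliest date of either not requiring oxygen support or hospital discharge". SAP section 2 sets the null for Hypothesis 1 as a BLD2660/Placebo hazard ratio of at least 1, explained as no shortening of recovery time. It states the alternative as "Hazard Ratio (BLD2660/Placebo) < 1 , indicating that treatment does reduce the time to recovery compared to placebo control". Success on either of the two primary hypotheses makes the study a success.

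SAP section 3 sizes the trial for a halving of the time to improvement, written as "i.e., hazard ratio[BLD2660/Placebo] of 0.5) with a two-sided 5% significance level". It describes theta in the events formula as one that "is the inverse of the log hazard ratio, as we are modeling improvement", prints it as 1/log(0.5), and adds that "the probability of observing an event is 0.60". Protocol 9.2 has "a 50% reduction in the time to clinical improvement, (i.e., hazard ratio of 0.5", with neither arm named as numerator. Protocol 9.1 tests HR = 1 against HR ≠ 1, with no direction.

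On sidedness, SAP 5.1 says "All p-values will be 1-sided and reported to 3 decimal places", SAP 5.10 monitors each primary endpoint at one-sided 2.5%, and SAP section 1 says "If there are any discrepancies between the protocol and SAP, this SAP will prevail". SAP 5.5.2 specifies the Cox model and the log-rank tests but states neither the direction of the ratio nor the tail.

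**The concern.** When the event is recovery, a shorter time to event is a higher event hazard. A beneficial drug therefore has HR (BLD2660/Placebo) above 1, and both the null and the alternative in SAP section 2 are reversed against their own explanations. Nothing elsewhere in either document redefines the ratio as Placebo/BLD2660 or as a ratio of times.

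Under the protocol's two-sided hypothesis a mislabelled ratio would leave the p-value unchanged. The SAP makes the hypothesis directional and the p-values one-sided. Since 5.5.2 names no tail, section 2 is the only formal statement of the rejection region for this test. A programmer who codes the inequality and a reader who follows the explanation would draw opposite conclusions from the same data.

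**Working it through.** **Inputs.** 75 events, 80% power, two-sided 5%, control fraction 1/3 and event probability 0.60 (SAP section 3); placebo median 12–15 days (SAP section 3, protocol 9.2); one-sided 2.5% (SAP 5.10), which has the same 1.96 cut-off for benefit as two-sided 5%.

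**1. The plan's event count.** d = (z_α/2 + z_β)² / [π(1 − π)θ²], with (1.960 + 0.842)² = 7.849 and π(1 − π) = 2/9.
- θ = log(2) = 0.693: d = 7.849 / (0.2222 × 0.4805) = 73.5, so 74 events, in line with the target of 75.
- θ = 1/log(0.5) = −1.443, as printed: d = 7.849 / (0.2222 × 2.081) = 17.0.

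So the target came from the log hazard ratio, not its reciprocal. Only θ² enters, so HR 0.5 and HR 2 give the same count.

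**2. What halving the time means.** With exponential times (an assumption), HR (BLD2660/Placebo) = placebo median / active median.
- Halved time: 12/6 = 15/7.5 = 2.
- The printed HR of 0.5: active median 12/0.5 = 24 to 15/0.5 = 30 days, a doubling.

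Cox fits to data simulated with medians of 15 and 7.5 days, 40 and 80 participants and censoring at Day 28 gave a median HR of 1.99.

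**3. Rejection probabilities by tail.** The standard error of log HR is 1/√(75 × 2/9) = 1/4.082.

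| True HR (BLD2660/Placebo) | Mean z | Rejects for HR > 1 (intended) | Rejects for HR < 1 (printed) |
|---|---|---|---|
| 2 | 0.693 × 4.082 = 2.83 | Φ(2.83 − 1.96) = 0.808 | Φ(−1.96 − 2.83) = 8.4e-7 |
| 1 | 0 | 0.025 | 0.025 |
| 0.5 | −2.83 | 8.4e-7 | 0.808 |

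**4. On the observed scale.** The critical HR is exp(±1.96/4.082): at least 1.62 in the intended tail, at most 0.62 in the printed one. An observed HR of 2 gives one-sided p = 1 − Φ(2.83) = 0.002 in the intended tail and 0.998 in the printed tail.

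**5. Event probability (minor).** 0.60 × 120 = 72 events, where √(72 × 2/9) = 4.0 and power is Φ(0.693 × 4.0 − 1.96) = 0.792. The stated 75 of 120 is 0.625. Going the other way, 73.5/0.60 = 122.5 participants against 120 planned.

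**The case against.** The strongest reply is that nobody would be misled. Section 2 puts the direction in words beside each inequality, section 3 remarks that improvement is being modelled, and the Kaplan-Meier curves would show which arm recovers sooner. The conditional-power formula in SAP 5.10 treats a large positive z as success for both endpoints. On this view it is a labelling slip, and the extreme probabilities belong to a reading nobody intends. Much of that stands: the intent is clear, and the figures in steps 3 and 4 describe only the literal reading. But the formal statement of a primary hypothesis should not need its explanation to overrule it, and the 5.10 formula does not settle the matter because the sign of z is never defined for this endpoint.

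A second reply is that SAP section 1 also sends changes in primary analyses through a protocol amendment, and section 3 still cites two-sided 5%, so the two-sided test in protocol 9.1 may govern. Even so, the p-values reported under SAP 5.1 are one-sided and need a direction.

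Two narrower points are fair. The 0.5 in protocol 9.2 is unlabelled rather than inverted, and it reads correctly as Placebo/BLD2660. The theta and 0.60 discrepancies are separate slips with no bearing on direction.

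**Conclusion.** The concern holds. SAP section 2 states Hypothesis 1 in the wrong direction, section 3 repeats it with a labelled ratio, and protocol 9.2 leaves the ratio unlabelled. This is an error of statement, not of design: 75 events, 80.8% power at HR 2 and 120 participants are unaffected, and the 1.96 cut-off for benefit is not in dispute.

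It still must be corrected. It reverses the rejection region of a one-sided test that can declare success alone. Taken literally, a true benefit of the design size would almost never succeed and the opposite effect would succeed 81% of the time. The reversal itself needs no assumption beyond the endpoint definition. The probabilities assume a Wald test with 75 events and 2:1 allocation, and equating halved time with HR 2 assumes exponential times.

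**What to change.** - **SAP section 2:** state H0: HR (BLD2660/Placebo) ≤ 1 and H1: HR > 1. Alternatively keep the printed inequalities and define the ratio as Placebo/BLD2660 throughout.
- **SAP section 3:** give the design alternative as HR (BLD2660/Placebo) = 2, equivalently Placebo/BLD2660 = 0.5. Replace θ = 1/log(0.5) with θ = log(2). Reconcile the 0.60 event probability (72 events) with the assumption of at least 75 of 120.
- **SAP 5.5.2:** state that the Cox and log-rank p-values are one-sided for HR (BLD2660/Placebo) > 1 at 2.5%.
- **SAP 5.6.2:** carry the same direction to time to discharge readiness, which borrows the primary method and states no direction of its own.
- **Protocol 9.2:** label the 0.5 as Placebo/BLD2660, or give 2 as BLD2660/Placebo.

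The cost is wording in four SAP sections and one label in the protocol. Event target, sample size, model and estimate stay as they are. The correction should be documented before the final unblinded analysis.
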